#### 6. GENERAL ANALYSIS DEFINITIONS

#### 6.1 **TREATMENT**

It is planned to include approximately 5 patients in this trial. All patients will receive idarucizumab (short label: Ida), which will be administered intravenously as two equal consecutive infusions over 5 to 10 minutes each or as two bolus injections no more than 15 minutes apart.

The residual effect period (REP) is defined as 1 day after the last trial medication application. The following treatment period will be defined:

- Screening: day of informed consent to day of first idarucizumab administration. If same day, then the period before first vial administration of idarucizumab.
- On-treatment: time of first administration of idarucizumab to time of last administration of idarucizumab + 1 day.
- Post-treatment: time after last idarucizumab administration + 1 day, to day of end of trial visit (Visit 5) or consent withdraw.

As it may take up to 5 days for some potentially drug related reactions to show up, 5-day REP will also be considered as sensitivity analysis.

#### 6.2 IMPORTANT PROTOCOL VIOLATIONS

No per protocol set will be defined for this study; however patients with potentially important protocol violations (IPVs) will be documented. The following is the list of potentially IPVs.

Cat	egory /	Description	Requirements	Excluded
Coc	le			from
Α	A Entrance criteria not met			
	A1.1	Inclusion criterion 2 for Group A or B not met	Patient not currently treated with dabigatran etexilate in the context of a clinical trial with dabigatran etexilate (1160.106 or 1160.108)	PDS
	A1.2	Inclusion criteria 1, 3, and/or 4 for Group A or B not met	Inclusion criteria 1, 3, and /or 4 not met as specified in the protocol.	PDS
	A2	Exclusion criteria not met	Exclusion criteria not met as specified in the protocol	PDS
В		Informed consent		
	B1	Informed consent/assent not available/not done	Informed consent/assent date missing	All
	B2	Informed consent/assent too late	Informed consent/assent date < actual consent/assent date > was after Visit 1 date < Visit 1 date >	None
С		Trial medication and randomisation		
	C1	Incorrect amount of trial medication taken	Only one vial or more than two vials of idarucizumab was administered.	None
KE	C2	Actual dose given and the dose based on patient's body weight do not match	Actual dose given collected in eCRF and the dose based on patient's body weight (see CTP Table 4.1.2: 1) do not match	None

Table 6.2: 1Important protocol violations

KEY: PDS – Pharmacodynamic set

All categories listed in Table 6.2: 1 will be checked automatically. Additional IPVs may be identified manually during the course of the study and will be assessed during the Medical and Quality Review meetings (MQRM). If the list of IPVs needs to be enlarged, it will be documented in the Blinded Report Planning Meeting (BRPM) / Database Lock Meeting minutes before database lock.

#### 6.3 PATIENT SETS ANALYSED

Two analysis sets will be used for the data analysis in this trial:

- Treated set (TS): includes all patients who received any dose of idarucizumab. The TS will be used to assess safety, clinical endpoints, demographics and baseline characteristics, concomitant diagnosis/therapy and medical history, as well as PK endpoints and ADA.
- Pharmacodynamic set (PDS): comprises all patients in the TS who provided at least one evaluable pre-dose and at least one post-dose observation for PD endpoints or biomarker measures. The PDS will be used for PD endpoint analyses. Note that for different PD endpoints or biomarkers, the number of evaluable patients may be different.

	Patient set		
Class of endpoint	Treated set	PDS	
Primary endpoints	Х		
Secondary and further endpoints	Clinical endpoints; idarucizumab PK endpoint*; ADA	Dabigatran PK endpoint; PD endpoints (biomarkers)	
Safety endpoints	Х		
Demographic/baseline endpoints	Х		

Table 6.3: 1Patient sets analysed

\* Only if at least one post-dose evaluable blood sample is available.

#### 6.5 **POOLING OF CENTRES**

This section is not applicable because centre/country is not included in the statistical model.

#### 6.6 HANDLING OF MISSING DATA AND OUTLIERS

With respect to efficacy and safety evaluations, it is not planned to impute missing values. The reversal of anticoagulation cannot be defined if either the pre-dose or all post-dose coagulation test is missing, or if the pre-dose coagulation test is below the ULN. Patients in such case will be considered as not evaluable for the corresponding biomarker.

#### Boehringer Ingelheim TSAP for BI Trial No: 1321.7

Proprietary confidential information © 2017 Boehringer Ingelheim International GmbH or one or more of its affiliated companies

Missing or incomplete AE dates will be imputed according to BI standards (see "Handling of missing and incomplete AE dates") (2).

Handling of missing PK data will generally be performed according to the BI standards (3).

Drug concentration data identified with below the lower limit of quantification (BLQ) will be displayed as such and not replaced by zero at any time point (this rule also applies to the lag phase, including the pre-dose values) with the exception of unbound sum dabigatran. For this analyte, data identified with BLQ following the administration of idarucizumab may be replaced with the lower limit of quantification, until measurable concentrations re-occur.

The appropriate time frame will be decided by the Trial Clinical Pharmacokineticist (TCPK) and described in the CTR.

With respect to pharmacodynamic evaluations it is not planned to impute missing values. However, clotting times may exceed the maximum clotting time of 500s recorded by the coagulometer, indicating the presence of high concentrations of dabigatran, for example in pre-dose idarucizumab samples. If the blood clotting time exceeds 500s, above the upper limit of quantification (ALQ) will be reported. For calculation of reversal of the anticoagulation effect, ALQ values may be replaced by 500s. In that case ALQ values will be discussed on an individual basis within the trial team (including TCM, Trial Biomarker Analyst (TBMA), TCPK and Trial Statistician (TSTAT) and decisions will be documented in the CTR. There are no rules for evaluation. BLQ values as well as pharmacodynamic data identified with no sample available (NOS), no valid result (NOR), and not analysed (NOA) will not be considered.

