#### 7.5.2 Other Secondary endpoints

Percent change from baseline of coagulation tests (dTT and ECT) at 30 minutes post-dose will be summarized descriptively or listed only if deemed appropriate.

Reversal of the anticoagulant effect of dabigatran at time t is defined as:

$$Reversal (t) = \frac{predose coagulation test - postdose coagulation test at time t}{predose coagulation test - ULN} \times 100\%$$

Values equal to or higher than 100% will be interpreted as complete reversal of the anticoagulant effect. The reversal of anticoagulant activity will be based on central lab measurements and calculated for coagulation tests, dTT and ECT, separately. Reversal cannot be defined for patients with dTT or ECT pre-dose measurement value less than ULN; such patients are considered as not evaluable for reversal related endpoints. The ULN was determined by using data from studies 1321.1 and 1321.2, calculated as the (arithmetic) mean +2 \* standard deviation (SD) by using all data collected prior to the dosing of dabigatran and the data from patients who were on placebo, as well as pre-dose data from idarucizumab alone treatment (as available).

Time to achieve complete reversal will be reported by listing the calculated reversal values at planned time points and using flags to show whether complete reversal is achieved at planned time points.

Duration of complete reversal, defined as the time period from when a patient first achieves complete reversal, up to the earliest time point among the following: middle point between last observation of 100% reversal and subsequent observation, 24 hours post-dose or re-

starting the treatment of dabigatran or other anticoagulation. Duration of complete reversal can be defined only for those patients who achieved complete reversal.

For Group A patients only, the cessation of bleeding within 24 hours will be reported in a listing.

For Group A patients only, bleeding status will be assessed during treatment period and be summarized descriptively or listed only if deemed appropriate. Other clinical conditions that may contribute to bleeding (Group A patients only) during the trial, such as major trauma or the use of antiplatelets, will also be reported.

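### Post-dose clotting times below the quantification limit are set aside as if missing, although the plan's own formula would score them as complete reversal (low priority)

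*SAP*

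**What the plan says.** The last sentence of the pharmacodynamic paragraph in SAP 6.6, which Protocol 7.5 also carries, reads: "BLQ values as well as pharmacodynamic data identified with no sample available (NOS), no valid result (NOR), and not analysed (NOA) will not be considered". The same paragraph states: "With respect to pharmacodynamic evaluations it is not planned to impute missing values". BLQ drug concentrations have their own rule earlier in the section, so this sentence concerns clotting times.

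The other limits are handled differently. At the top of the clotting range: "For calculation of reversal of the anticoagulation effect, ALQ values may be replaced by 500s", after case-by-case discussion. For unbound sum dabigatran after idarucizumab, a BLQ concentration may be set to the LLOQ.

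SAP 7.5.2 defines reversal at time t as (pre-dose − post-dose)/(pre-dose − ULN) × 100%, separately for dTT and ECT, and adds: "Values equal to or higher than 100% will be interpreted as complete reversal of the anticoagulant effect". On the ULN it says: "The ULN was determined by using data from studies 1321.1 and 1321.2". It is a mean plus 2 SD of clotting times without dabigatran effect. Neither document gives its value, or an LLOQ for any clotting test.

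On evaluability, SAP 6.6 says: "The reversal of anticoagulation cannot be defined if either the pre-dose or all post-dose coagulation test is missing". A pre-dose value under the ULN has the same effect. The consequence is stated next: "Patients in such case will be considered as not evaluable for the corresponding biomarker". SAP 6.3 defines the pharmacodynamic set (PDS) as one that "comprises all patients in the TS who provided at least one evaluable pre-dose and at least one post-dose observation for PD endpoints". A biomarker measure also counts, and the number evaluable may differ by biomarker.

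**The concern.** A BLQ clotting time carries information: the sample clotted faster than the assay can quantify. NOS, NOR and NOA carry none. Putting all four under one rule makes a post-dose value disappear because it is short, and a short clotting time is what the reversal endpoints are meant to detect. The data loss is then tied to the outcome.

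Protocol 5.5.2 makes the coagulation biomarkers the basis for judging efficacy. With about 5 patients planned, one child's lost or wrong entry is 1/5 = 20% of the evidence on that endpoint. Listings do not remove the problem, because the reversal values, flags and durations in them are derived under this rule.

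**Working it through.** There is no stated figure to reproduce, since the sample size rests on feasibility. The check applies the plan's own definitions.

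**Step 1: what a BLQ value means.** With pre-dose above the ULN, (pre − post)/(pre − ULN) ≥ 1 is the same as post ≤ ULN. So if LLOQ ≤ ULN, every post-dose BLQ is complete reversal. The endpoint presupposes that ordering. With assumed ULN 40 s, pre-dose 120 s and LLOQ 44 s, the best quantified result would be (120 − 44)/(120 − 40) = 95%, and no quantified value could ever reach 100%.

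**Step 2: range.** Assume ULN 30 to 50 s, pre-dose 60 to 500 s and LLOQ 50% to 100% of the ULN. Reversal calculated at the LLOQ then runs from 100% (LLOQ = ULN) to (60 − 25)/(60 − 50) = 350%. It is never below 100%.

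**Step 3: effect on the derived endpoints.** Assume ULN 40 s, pre-dose 120 s, LLOQ 32 s, no anticoagulant restarted before 24 h, and no usable between-vials sample.

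- At the LLOQ: reversal (120 − 32)/80 = 110%; percent change (32 − 120)/120 = −73.3%.
- At 36 s: reversal 84/80 = 105%. At 60 s: reversal 60/80 = 75%.

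SAP 7.5.2 ends the duration at the earliest of three points: the midpoint between the last 100% observation and the next observation, 24 h, or restart of anticoagulation.

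| Results for one test | BLQ kept at LLOQ | BLQ dropped |
|---|---|---|
| Full schedule: BLQ, BLQ, 36 s, 60 s at 0.5, 4, 12, 24 h | Complete from 0.5 h; ends (12 + 24)/2 = 18 h; duration 17.5 h | First flag at 12 h; ends 18 h; duration 6.0 h |
| Reduced schedule: BLQ at 0.5 h, 60 s at 24 h | Complete at 0.5 h; ends (0.5 + 24)/2 = 12.25 h; duration 11.75 h | No complete reversal |
| Reduced schedule: BLQ at both times | Duration 24 − 0.5 = 23.5 h | Not evaluable for that test |

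In every row the 30-minute percent change is also lost for that test. The reduced schedule is the one in Protocol Tables 10.3: 2 and 10.3: 4, which keep biomarkers only at pre-dose, 30 minutes and 24 hours.

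**Step 4: how often, for illustration only.** Suppose each post-dose sample is BLQ with probability q, independently. All post-dose values of a test are then BLQ with probability q⁴ on the full schedule and q² on the reduced one.

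| q | All BLQ, per child: full / reduced | At least 1 of 5 children: full / reduced | 30-minute value lost in at least 1 of 5 |
|---|---|---|---|
| 0.10 | 0.01% / 1% | 0.05% / 4.9% | 1 − 0.9⁵ = 41% |
| 0.25 | 0.4% / 6.25% | 1.9% / 27.6% | 1 − 0.75⁵ = 76% |

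The documents give no basis for choosing q. Results within one child are probably positively correlated, which would raise the all-BLQ figures.

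**The case against.** The strongest reply is that the rule may hardly ever operate. The ULN was computed from measured clotting times without dabigatran effect, so normal values were evidently quantifiable for the most part. Complete reversal means a return to that range; a BLQ result needs clotting faster than the assay can report. The assumed limits are also demanding. If normal values are roughly symmetric and few fall below 32 s, mean − 2 SD ≥ 32 and mean + 2 SD = 40 force an SD of at most (40 − 32)/4 = 2 s. This objection stands: frequency cannot be derived from the documents, and the durations above are illustrations.

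A reader might also infer more than the text supports:

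- *That the child drops out of the PDS.* SAP 6.6 makes the child not evaluable only for the biomarker concerned. Four biomarkers are measured, and under SAP 6.3 the child stays in the PDS if another one is evaluable.
- *That a delayed time to reversal would be reported.* SAP 7.5.2 lists reversal values and flags by planned time point, so a dropped value appears as a visible gap. A quantifiable between-vials sample at or below the ULN would show reversal earlier still and protect the duration in the first row of Step 3. Tables 10.3: 2 and 10.3: 4 omit that sample.

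Neither document defines BLQ for the clotting assays, so it could be said that such a result may be an artefact. That carries less weight, because the plan has a separate code for invalid results (NOR).

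Finally, the endpoints are secondary and descriptive, and any error is conservative. That limits the priority, but it does not make a listing accurate when it shows a reversed child as not reversed.

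**Conclusion.** The point holds as a defect in a stated rule, at low priority. Where LLOQ ≤ ULN, the sentence discards results that the plan's own formula scores as complete reversal. This is out of line with how the plan treats ALQ clotting times and BLQ unbound dabigatran, and nothing elsewhere in either document corrects it.

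When such a value occurs, the affected test loses its 30-minute percent change or a reversal flag, and its duration can be understated. On the two-sample schedule a reversed child can be listed as never reversed, or as not evaluable for that biomarker. The documents do not support a claim that this will be common or that it will materially distort the trial's results. The primary safety endpoint is untouched, and no inference is planned. The conclusion rests on LLOQ ≤ ULN and on reading BLQ as a valid result distinct from NOR; the hours and percentages rest on the assumed limits.

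**What to change.** In SAP 6.6, treat only NOS, NOR and NOA as missing. For a post-dose BLQ clotting time where LLOQ ≤ ULN, and where the patient is otherwise evaluable, flag complete reversal, calculate reversal and percent change at the LLOQ, and list them as bounds (at least x% reversal, at least y% decrease). State the LLOQ and ULN for dTT and ECT. A pre-dose BLQ stays not evaluable for reversal, because it lies below the ULN. Since Protocol 7.5 carries the same sentence, record the departure in SAP section 4.

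One footnote is needed. If the pre-dose value was ALQ and set to 500 s, the complete-reversal flag still stands, but the reversal percentage is no longer a strict lower bound: it equals 1 + (ULN − post)/(pre − ULN), which falls towards 100% as the true pre-dose value rises.

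The cost is a revised sentence, the two limits and a listing footnote, with no new data. The downside is that a few values appear as bounds rather than exact numbers.

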#### 6.7 BASELINE, TIME WINDOWS AND CALCULATED VISITS

Unless otherwise specified, baseline value will be the last available measurement taken prior to administration of idarucizumab (same day is allowed).

### 7. PLANNED ANALYSIS

This trial has a single treatment group with no control group. Approximately 5 patients will be enrolled in this trial. The primary and secondary endpoints will be reported using descriptive statistics or using listings due to limited number of patients in each group. Descriptive statistics will be performed by patient groups (patients having life-threatening or uncontrolled bleeding and those requiring emergency surgery/urgent procedures) and together, when appropriate from a sample size perspective. Statistical inference will not be performed.

Descriptive statistics for continuous variables will generally be N (number of patients with non-missing values), mean, standard deviation (SD), minimum, median, and maximum. In general, means, medians, SDs, will be presented to one more decimal place than the raw data. Minimums and maximums will be presented to the same number of decimal places as the raw data. Geometric means and geometric coefficients of variation will be used in summaries of PK/PD data.

Tabulations of frequencies for categorical data will include all possible categories and will display the number of observations in a category as well as the percentage (%) relative to the respective treatment group (unless otherwise specified, all patients in the respective patient set whether they have non-missing values or not). Percentages will be rounded to one decimal place. The category missing will be displayed only if there are actually missing values.

If patients entered the trial more than once (i.e. patients need a reversal of the anticoagulant effect of dabigatran again for a new and independent event), each time will be treated as an independent case. The patient will be assigned different patient identification number for each time of enrolment. The cases will be analysed independently as if from different patients. This is only possible for patients from group B.

#### 7.1 DEMOGRAPHIC AND OTHER BASELINE CHARACTERISTICS

Demographic and baseline characteristics will be summarized descriptively or listed only depending on the number of patients.

#### 7.2 CONCOMITANT DISEASES AND MEDICATION

The concomitant medications taken at baseline and those taken while on treatment will be coded using the WHO Drug coding dictionary. These will be listed by patient.

Listing of patients' exposure to dabigatran prior to entering the trial will be presented, including the time of last dabigatran intake, daily dose and dabigatran indication.

Medical history and baseline disease will be listed, as well as the baseline bleeding assessment.

#### 7.3 TREATMENT COMPLIANCE

Only a listing is planned for this section of the report. The information on the start and end date and time of each vial of idarucizumab and actual administered volume will be provided.

#### 7.4 PRIMARY ENDPOINTS

There is no primary efficacy endpoint.

As the primary safety endpoints, occurrence of drug-related adverse events (including immune reactions) and all-cause mortality during the trial (from the start of dosing until 30 days after the end of dosing) will be listed. Reason of death will be also listed.

Potential specific risks that could be caused by ADA, such as local injection site reactions, systemic hypersensitivity, including anaphylaxis or immune complex disease, are considered as immune reactions, and will be assessed clinically and listed.

As to summaries of other adverse events, refer to Section 7.8.1.

#### 7.5 SECONDARY ENDPOINTS

Secondary endpoints will be listed based on treated set or pharmacodynamic set according to the nature of endpoints.

#### 7.5.1 Key secondary endpoints

This section is not applicable as no key secondary endpoint has been specified in the protocol.

#### 7.5.2 Other Secondary endpoints

Percent change from baseline of coagulation tests (dTT and ECT) at 30 minutes post-dose will be summarized descriptively or listed only if deemed appropriate.

Reversal of the anticoagulant effect of dabigatran at time t is defined as:

$$Reversal (t) = \frac{predose coagulation test - postdose coagulation test at time t}{predose coagulation test - ULN} \times 100\%$$

Values equal to or higher than 100% will be interpreted as complete reversal of the anticoagulant effect. The reversal of anticoagulant activity will be based on central lab measurements and calculated for coagulation tests, dTT and ECT, separately. Reversal cannot be defined for patients with dTT or ECT pre-dose measurement value less than ULN; such patients are considered as not evaluable for reversal related endpoints. The ULN was determined by using data from studies 1321.1 and 1321.2, calculated as the (arithmetic) mean +2 \* standard deviation (SD) by using all data collected prior to the dosing of dabigatran and the data from patients who were on placebo, as well as pre-dose data from idarucizumab alone treatment (as available).

Time to achieve complete reversal will be reported by listing the calculated reversal values at planned time points and using flags to show whether complete reversal is achieved at planned time points.

Duration of complete reversal, defined as the time period from when a patient first achieves complete reversal, up to the earliest time point among the following: middle point between last observation of 100% reversal and subsequent observation, 24 hours post-dose or re-

starting the treatment of dabigatran or other anticoagulation. Duration of complete reversal can be defined only for those patients who achieved complete reversal.

For Group A patients only, the cessation of bleeding within 24 hours will be reported in a listing.

For Group A patients only, bleeding status will be assessed during treatment period and be summarized descriptively or listed only if deemed appropriate. Other clinical conditions that may contribute to bleeding (Group A patients only) during the trial, such as major trauma or the use of antiplatelets, will also be reported.

The blood sample for idarucizumab ADA is scheduled to be collected prior to vial 1 administration and at Day 30 post-dose. If a patient doesn't have ADA pre-dose and has ADA at Day 30, this patient is considered as having treatment-emergent ADA. Development of treatment-emergent ADA with cross reactivity to idarucizumab at 30 days post-dose of idarucizumab will be reported using a binary outcome (Yes/No).

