4.2 OTHER TREATMENTS, EMERGENCY PROCEDURES, RESTRICTIONS

4.2.1 Other treatments and emergency procedures

For patients who continue to bleed, supportive care with blood products such as fresh frozen plasma, fresh or packed red blood cells, or packed platelets are permitted. Administration of activated prothrombin complex concentrates (e.g. FEIBA) or recombinant Factor VIIa, or concentrates of coagulation factors II, VII, IX, or X may be considered, even though their use has not been evaluated in clinical trials. Dabigatran can be haemodialysed out of the patient's circulation. Approximately 60% of the drug can be removed over 2-3 hours: however, there is limited clinical data supporting this approach (P13-01830, P13-04186).

Page 35 of 77

Proprietary confidential information © 2016 Boehringer Ingelheim International GmbH or one or more of its affiliated companies

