7.2 NULL AND ALTERNATIVE HYPOTHESES

There is no hypothesis testing for this trial.

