7.7 DETERMINATION OF SAMPLE SIZE

The design of this trial (including the definition of endpoints and sample size) has been agreed with the European Medicines Agency's Paediatric Committee.

Sample size (approximately 5 patients) is determined based on feasibility.

Page 59 of 77

Proprietary confidential information © 2016 Boehringer Ingelheim International GmbH or one or more of its affiliated companies

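### Duration of complete reversal stops when anticoagulation is restarted but not when haemodialysis starts, so reversal maintained by dialysis could be counted as idarucizumab duration

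*SAP*

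**What the plan says.** SAP 7.5.2 starts the duration when complete reversal is first achieved and runs it "up to the earliest time point among the following: middle point between last observation of 100% reversal and subsequent observation, 24 hours post-dose". The remaining end point is re-"starting the treatment of dabigatran or other anticoagulation" (the prefix falls before a page break). These are the only stop events in the definition.

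Protocol 4.2.1, on other treatments and emergency procedures, states: "Dabigatran can be haemodialysed out of the patient's circulation". It adds: "Approximately 60% of the drug can be removed over 2-3 hours: however, there is limited clinical data supporting this approach". For patients who continue to bleed, the same section allows blood products and says that factor concentrates and recombinant Factor VIIa may be considered.

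Protocol 5.2 makes central dTT and ECT, with other coagulation tests and unbound dabigatran, the basis for judging idarucizumab efficacy. Cessation of bleeding in Group A is a binary outcome in protocol 7.3.2 and a 24-hour listing in SAP 7.5.2. SAP 7.2 lists concomitant medications by patient, coded with WHO Drug.

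**The concern.** The SAP already accepts that another treatment acting on the same clotting tests should end the count, because restarting an anticoagulant does so. It applies this only to treatment that would shorten apparent reversal. Dialysis acts the other way: it removes dabigatran, so it can hold dTT and ECT below the ULN after idarucizumab alone would have stopped doing so. Under the written rule that extra time becomes part of the idarucizumab duration.

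The endpoint is meant to describe the period up to 24 hours, and the adult data in protocol 1.1 show dabigatran re-emerging in some patients during that period. In a case series of about 5, one patient's derived duration is a visible share of the evidence. Dialysis is also a procedure, so a listing of coded drugs may not show it.

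**Working it through.** The plan has no figure to reproduce: "Sample size (approximately 5 patients) is determined based on feasibility", and "There is no hypothesis testing for this trial". The check applies the SAP 7.5.2 rule to the planned sampling times.

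**Inputs**
- Post-dose samples at 0.5, 4, 12 and 24 h (protocol 6.2.2 and 6.2.3, nominal times).
- Complete reversal first seen at 0.5 h (assumption).
- Stop events as in SAP 7.5.2.

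**Formula:** duration = earliest stop time − time of first complete reversal.

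**Without dialysis**
- Reversal held at every sample: 24 − 0.5 = 23.5 h.
- Loss first seen at 12 h: midpoint (4 + 12)/2 = 8 h, so 8 − 0.5 = 7.5 h.
- Loss first seen at 24 h: midpoint (12 + 24)/2 = 18 h, so 18 − 0.5 = 17.5 h.

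**Dialysis prevents that loss, current rule:** 23.5 h is recorded.
- Excess if the loss would have been seen at 12 h: 23.5 − 7.5 = 16 h.
- Excess if the loss would have been seen at 24 h: 23.5 − 17.5 = 6 h.
- Excess if no loss would have occurred: 0 h.

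The excess does not depend on the assumed start, which cancels (24 − 8 and 24 − 18). A loss already visible at 4 h would give a midpoint of 2.25 h, a duration of 1.75 h and an excess of 21.75 h. Dialysis would have to act within 4 h of dosing to mask it, so I leave it outside the working range.

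**Dialysis as a stop event, reversal held at every sample**

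| Dialysis starts (h) | Current rule (h) | With stop (h) |
|---|---|---|
| 2 | 23.5 | 1.5 |
| 5 | 23.5 | 4.5 |
| 8 | 23.5 | 7.5 |
| 13 | 23.5 | 12.5 |

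For comparison, restarting an anticoagulant at hour 5 already gives 5 − 0.5 = 4.5 h under the current rule.

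**Does the window matter?** Protocol 1.1 reports that 93% of adults at 12 h and 79% at 24 h had unbound dabigatran below 20 ng/mL. If those rates held in children (an assumption), the chance that at least one of 5 is not below that level is 1 − 0.93^5 = 30% at 12 h and 1 − 0.79^5 = 69% at 24 h. For 3 to 8 patients the 24 h figure runs from 51% to 85%. The threshold is a concentration, not a loss of 100% reversal, so this shows only that re-emergence is plausible.

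**Could dialysis mask it?** If 60% removal applied in proportion to the unbound concentration, a level of up to 20/(1 − 0.6) = 50 ng/mL would fall to 20 ng/mL. The documents do not say that it does, and the 6 to 16 h range does not depend on it.

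**The case against.** The strongest reply is that stopping at dialysis creates the opposite error. A patient dialysed at hour 5 with complete reversal still measured at 24 h would be given 4.5 h, although true reversal on idarucizumab alone is unknown and at least that long. This stands against replacing one number with the other. It does not stand against showing both and flagging the shorter one as censored, and the SAP already truncates in the same way for restarted anticoagulation.

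It is also fair that the results are descriptive, that no inference is made, and that a reader can compare listings for about 5 patients. The protocol itself calls the dialysis data limited, and does not say that the 60% holds for dabigatran bound to idarucizumab. These points limit the size of the concern. They do not supply the missing stop event.

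Three stronger readings are tempting, and the documents do not support them:

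- **A reader might infer that cessation of bleeding takes no account of factor concentrates.** Concomitant therapies are recorded at every visit, and medications are listed by patient (SAP 7.2). Protocol 3.1 separates pharmacological reversal from clinical management, and protocol 5.1.2 marks cessation as a safety matter, with no claim of attribution to the drug. The SAP abbreviations include PCC, which the visible text never uses, and the further-endpoint sections are not in the public version, so specific handling cannot be ruled out.
- **A reader might infer that any error must favour idarucizumab.** It arises only if a co-treatment is given and changes the result. Protocol 5.7 reports little preclinical effect of concentrates on reversal. Their use in a patient who is still bleeding would itself signal incomplete haemostasis.
- **A reader might take all the time after dialysis starts as falsely credited.** That treats the start of dialysis as the true loss of reversal. In the adult data, 79% were still below 20 ng/mL at 24 h.

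**Conclusion.** The gap is real but small. The visible definition in SAP 7.5.2 ends duration at restarted anticoagulation and not at haemodialysis, so reversal maintained by dialysis within 24 hours would be counted as idarucizumab duration. The excess is 6 to 16 h for a patient in whom dialysis masks a loss that would first have been seen at 24 h or 12 h, and nil where no loss would have occurred.

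This rests on nominal sampling times, on dialysis after dosing and within 24 hours, and on dialysis being able to keep the tests at complete reversal. The documents give no frequency of dialysis, and the number of such patients may be zero. For cessation of bleeding the point is one of display only. Nothing here concerns whether or when these treatments should be used.

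**What to change.** In SAP 7.5.2, add start of haemodialysis after idarucizumab as a stop event for duration of complete reversal, flagged as censored. List each patient's duration with and without that stop. If dialysis starts before complete reversal is first observed, show the version with the stop as not defined. Confirm that the concomitant-therapy record captures the start time of dialysis, since a drug-coded listing may not.

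As a display aid only, print beside the Group A cessation-of-bleeding result the times of any blood product, factor concentrate, Factor VIIa, surgery or dialysis. Do not add a rule that declares cessation after any of these non-attributable.

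The cost is one more listing column for duration, the co-treatment times beside the cessation result, and a shorter censored duration for a dialysed patient. That shorter value may understate the true effect, which is why both versions should be listed.
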